7.2 Adjustments for Covariates

For efficacy and exploratory variables adjustment for the respective baseline value and type of MI (STEMI or NSTEMI as collected in the IRT data base) will be performed.

In case there are at least 5% discrepancies for the type of MI between eCRF and IWRS data, a sensitivity analysis will be performed to assess the primary efficacy endpoint, the first secondary efficacy endpoint, the second secondary efficacy endpoint and the third secondary efficacy endpoint. The sensitivity analysis will consist in running the model using the covariate coming from the eCRF instead of IWRS.

7.3 Handling of Dropouts or Missing Data

Missing data will not be replaced. To handle missing data and unbalance datasets, the efficacy and exploratory variables will be analysed using the restricted maximum likelihood (REML) estimation.

Partial and completely missing dates will be imputed for study drug first dose date and study drug last dose date. Partial missing dates will be imputed for AE onset date/date becomes serious and AE/Concomitant Medication stop date. Missing start dates for concomitant medications will not be imputed. Imputation rules are described below:

Imputation of Study Drug First Dose:

First dose date and time are mandatory fields. No Imputations are expected.

Distribution:

Original:

Copy:

TPCA025 Version 2 (based on TPQA036 Version 2) Effective Date: 27th August 2017 Prior Effective Date: 21st December 2016

Sponsor:	AstraZeneca AB	Protocol/CIP Number:	D7550C00003
CIL Project Number:	40343		

In the rare cases of missing date, the first dose date of study drug will be imputed if all the following criteria are met:

- There is a missing or partial date for the first dose of study drug, and
- There is at least one kit for which the amount of drug dispensed does not equal the amount of drug returned, and
- The kits for which the amount of drug dispensed does not equal the amount of drug returned have complete non-missing dispensed date

If that is the case, first dose date of study drug will be defined as the earliest dispensed date from kits for which amount of drug dispensed does not equal the amount of drug returned. Missing time will be not replaced.

Imputation of Study Drug Last Dose:

Last dose date and time are mandatory fields. No Imputations are expected.

In the rare cases of missing date, the last dose date of study drug will be imputed if all the following criteria are met:

- There is a missing or partial date for the last dose of study drug, and
- There is at least one kit for which the amount of drug dispensed does not equal the amount of drug returned, and
- The kits for which the amount of drug dispensed does not equal the amount of drug returned have complete non-missing returned date.

If that is the case, last dose date of study drug will be defined as the latest returned date from kits for which amount of drug dispensed does not equal the amount of drug returned. Missing time will be not replaced.

Imputation of AE Onset Date and AE becomes serious date:

Missing onset dates (where UN, UNK and 0000 indicate unknown or missing Day and Month and Year respectively for partial missing dates; while completely missing dates would be left empty):

- Completely missing dates will be not imputed
- If the day is missing and the month and year are different from the month and year of the first dose of study drug, assume YYYY-MMM-01. If the month and year are the same as the first dose of study drug month and year and the end date (after any imputation) is on or after (including still on-going at the end of the study) the first dose of study drug, then assume the date of the first dose of study drug. If the month and year are the same as the first dose of study drug month and year and the end date (after any imputation) is prior to the first dose of study drug, then assume the end date of the first dose of study drug for the end date (after any imputation) is prior to the first dose of study drug, then assume the end date for the onset date.
- If the month is missing and the year is different from the year of first dose of study drug, assume YYYY-JAN-01 of the collected year. If the year is the same as the first dose of study drug year and the end date (after any imputation) is on or after (including still ongoing at the end of the study) the first dose of study drug, then assume the date of the first dose of study drug. If the year is the same as the first dose of study drug and the

TPCA025 Version 2 (based on TPQA036 Version 2) Original:

Copy:

Effective Date: 27th August 2017 Prior Effective Date: 21st December 2016

Sponsor:	AstraZeneca AB	Protocol/CIP Number:	D7550C00003
CIL Project Number:	40343		

end date (after any imputation) is prior to the first dose of study drug, then assume the end date for the onset date.

After applying these rules, if the imputed AE onset date is after a complete AE end date or date of death, the imputed onset date will be the same as the complete AE end date/ date of death.

With regard to the AE becomes serious date, if after applying all these rules the imputed AE becomes serious date is missing or before the AE start date, then the imputed AE becomes serious date will be the same as the AE start date.

Of note that missing start dates for concomitant medications will not be imputed.

Imputation of AE / Concomitant Medication Stop Date:

Missing stop dates (where UN, UNK and 0000 indicate unknown or missing Day and Month and Year respectively for partial missing dates; while completely missing dates would be left empty):

- Completely missing dates will be not imputed
- If the day is missing: Assume the last day of the month
- If the month is missing: Assume YYYY-DEC-31.

If the AE/CM is ongoing, the stop date will remain as missing. After applying these rules, if the imputed AE or CM stop date is after the date of death, the imputed stop date will be the same as the date of death. Except for the above and unless otherwise specified, complete missing data will not be imputed.

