6.2.2 Windows

For the purpose of statistical analysis and if not otherwise specified, all the efficacy variables (primary, secondary and exploratory variables) and all the safety variables (Clinical laboratory evaluations, ECGs, Vital Signs and Physical examinations) will be assigned to the visit in which they are collected depending on the following analysis visit windows.

Analysis visit (AVISIT)	Scheduled visit day	Visit Window for Analysis (Days)
Baseline ^b	1	<]ª
Baseline Post-dose ^c	1	1
Visit 3	14	$10 - 18$ and $\leq = $ last dose
Visit 4	28	23 - 33 and <= last dose + 3
Visit 4b	56	49 – 63 and <= last dose
Visit 4c	84	74 – 94 and <= last dose + 3
Visit 5 – FUP 1 month	56 / 112	>=last dose + 24

Table 3: Visit windows

^a Includes also measurements collected at day 1 prior to first dose of IP for all variables except PRO questionnaires, ECGs, Vital Signs and Physical examinations. For PRO questionnaires, ECGs, Vital Signs and Physical examinations, all the measurements collected at day 1 will be considered as baseline measurements as per protocol. For uLTE₄ and cardiovascular biomarkers, the baseline will be the last available value before the first dose of treatment, among the values collected after the ACS event +7 days (included).

^b Analysis visit will be labelled "Baseline Pre-dose" for PK measurements.

^c Only applicable to PK measurements occurring on Day 1 after the first dose.

Measurements collected outside the visit windows will be labelled as "Unscheduled visit". For uLTE₄, urine creatinine, Creatinine-normalized u-LTE₄ and Cardiovascular biomarkers, measurements collected from date of ACS event to 6 days post ACS will be labelled as "Screening".

Distribution:

Original:

Copy:

TPCA025 Version 2 (based on TPQA036 Version 2)

STATISTICAL ANALYSIS PLAN

Sponsor:	AstraZeneca AB	Protocol/CIP Number:	D7550C00003
CIL Project Number:	40343		

In general, the baseline value used for statistical analyses is the last available value among those in the Baseline visit windows, prior to first dose of IP, except for PRO questionnaires. Additional details for baseline assessment will be given in section 6.3.

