During the single-blind treatment period, subjects are supposed to take once daily if on high dose and once daily if on low dose of AZD5718 or matching placebo according to the dosing schedule. Overall compliance to the dosing schedule will be examined for subjects in the Safety Analysis Set.

The percent compliance is defined as the total number of tablets consumed divided by the total number of tablets that should have been taken:

- (Total number of tablets consumed) x 100 / [(Exposure) x 2] for subjects on of AZD5718 or matching placebo and
- (Total number of tablets consumed) x 100 / (Exposure) for subjects on AZD5718 or matching placebo

where, total number of tablets consumed will be calculated as: Total number of tablets dispensed – Total number of tablets returned. The quantity of study drug dispensed to and returned by the subject will be counted and recorded on the drug accountability eCRF page.

No replacement of missing data will be performed. Therefore, if one of the total number of tablets dispensed, total number of tablets returned, or duration of exposure is missing the resulting compliance will be missing.

Compliance will also be computed using the following categories:

- < 80%
- \geq 80% to < 120%
- ≥ 120%

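### SAP 7.3 replaces a partial last-dose date with the kit return date, even when the recorded month and year show that dosing ended earlier

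*SAP*

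**What the plan says.** SAP 7.3 (Imputation of Study Drug Last Dose) applies when three conditions hold. The first is "There is a missing or partial date for the last dose of study drug". The second is "There is at least one kit for which the amount of drug dispensed does not equal the amount of drug returned". The third is that the kits concerned have complete return dates. The imputed value is then fixed as follows: "last dose date of study drug will be defined as the latest returned date from kits for which amount of drug dispensed does not equal" what came back. A partial date and a wholly missing date get the same treatment. The section adds: "Last dose date and time are mandatory fields. No Imputations are expected".

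The other date rules in SAP 7.3 work differently. A partial AE onset date keeps its recorded month or year. A partial AE or medication stop date goes to the last day of the recorded month or, if the month is missing too, to the end of the recorded year. Both are also capped at death; for stop dates the cap applies "if the imputed AE or CM stop date is after the date of death".

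The last-dose date is then used in several places:
- SAP 6.2.2, Table 3: Visit 3 values must fall on or before last dose. The Visit 4 window is "23 - 33 and <= last dose + 3". Visit 4c has the same +3 day limit on Days 74 to 94. Visit 5 starts 24 days after last dose.
- SAP 6.2.3 and 6.6.2 to 6.6.4: the on-treatment phase for adverse events, laboratory values and other safety recordings ends 7 days after last dose.
- SAP 8.5: a concomitant medication must have started by the last dose.

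SAP 6.6.1 excludes imputed dates from exposure and actual exposure. Exposure is set to missing, and compliance is then missing as well.

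**The concern.** A recorded month and year is information about when dosing ended. The rule discards it and can assign a date that the eCRF rules out. The comparable rules in the same section do not do this.

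The error can reach the main analyses. Patients who stop drug are asked to continue their visits (Protocol 3.9), so off-drug samples will exist. The u-LTE4 model uses Visits 3, 4 and 4c (SAP 8.6.1) and the CFVR model uses Visits 4 and 4c (SAP 8.6.2). Table 3 is written to keep values taken well after last dose out of those visits, and a falsely late last dose lets them back in. The same date decides whether an adverse event or laboratory value counts as on treatment, which ECG is the last on-treatment one, and whether a medication counts as concomitant.

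**Working it through.** The documents state no figure to reproduce, and they give no frequency of partial last-dose dates. The check applies the SAP's own limits to constructed cases. First-dose dates are assumed, and visits are taken on their nominal days.

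Inputs: Table 3 windows (SAP 6.2.2), the last dose + 7 day on-treatment limit (SAP 6.2.3), and kit returns at Visits 4, 4b and 4c (Protocol Table 1).

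Formulas, with Day 1 as first dose:
- On-treatment end = last dose + 7.
- A Visit 3 value on Day d is kept if 10 ≤ d ≤ 18 and d ≤ last dose.
- A Visit 4 or 4c value is kept if d lies in the window and d ≤ last dose + 3.
- Minimum overstatement = imputed day − last day of the recorded month. It is a minimum because the month-end is the latest date that the record allows.

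| | Case A | Case B | Case C |
|---|---|---|---|
| First dose (assumed) | 24 March | 1 March | 1 March |
| Last dose as recorded | March | March | April |
| Bottle returned = imputed date | 20 April, Day 28 (Visit 4) | 25 April, Day 56 (Visit 4b) | 23 May, Day 84 (Visit 4c) |
| Last day of recorded month | Day 8 | Day 31 | Day 61 |
| Minimum overstatement | 28 − 8 = 20 days | 56 − 31 = 25 days | 84 − 61 = 23 days |
| On-treatment end, SAP rule | 28 + 7 = Day 35 | 56 + 7 = Day 63 | 84 + 7 = Day 91 |
| On-treatment end, month-end | 8 + 7 = Day 15 | 31 + 7 = Day 38 | 61 + 7 = Day 68 |

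Effect on the visit windows:
- Case A, Day 14 sample: the SAP rule keeps it (14 ≤ 28); the month-end excludes it (14 > 8).
- Case A, Day 28 sample: the SAP rule keeps it (28 ≤ 31); the month-end excludes it (28 > 8 + 3 = 11).
- Case B: Visit 4b has no urine or CFVR measurement, and the Day 28 sample is kept either way (28 ≤ 31 + 3 = 34). Only safety phase and medication class change; for example, adverse events starting on Days 39 to 63 become on treatment.
- Case C, Day 84 sample: the SAP rule keeps it (84 ≤ 87); the month-end excludes it (84 > 61 + 3 = 64).

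More generally, when the bottle is returned on the visit day, a Day 28 sample is wrongly kept if the true last dose was Day 24 or earlier (24 + 3 = 27). A Day 84 sample is wrongly kept if it was Day 80 or earlier (80 + 3 = 83). For a patient who takes the last dose at Visit 4c and returns the drug there, the error is 0 days.

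**The case against.** The strongest reply is that the rule will hardly ever be used. Last-dose date is a mandatory field. Dose dates and times are kept on diary cards that are reviewed at Visits 3, 4, 4b and 4c (Protocol 4.1 and 7.2). Patients who stop are asked to return cards and drug (Protocol 3.9.1), and missing data are queried (Protocol 9.4). This stands, and it is why the expected impact is small. It does not justify a contingency rule that contradicts the record when it is used.

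The second reply is that the error is mostly cautious. A late date places more adverse events on treatment. Off-drug values in the active arm would probably dilute the effect, and the protocol favours intention to treat with all available data. The point about direction is fair. But the SAP itself limits the visit windows by last dose, and this rule undoes that limit for the patients concerned.

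A reader might infer more than the documents support:
- That the patient is treated as dosed throughout. Not so for exposure, actual exposure or compliance (SAP 6.6.1).
- That the tablet count is ignored. It selects which kits qualify; what it does not do is bound the date.
- That the missing death cap distorts results. No sample or adverse event arises after death, and the interval from last dose to death is calculated only from complete dates (SAP 8.8.2).
- That affected patients tend to be early stoppers. Nothing in the documents shows this.

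**Conclusion.** The point holds for partial dates. SAP 7.3 can assign a last dose outside the recorded month and year, and that can move samples across the last dose and +3 day limits and safety data across the +7 day limit. In the constructed cases the date is at least 20 to 25 days late, and Visit 3, 4 or 4c samples change status in two of the three. The number of patients affected is unknown and probably very small, so this corrects a rule that is wrong as written and is no threat to the trial's conclusions.

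Two limits apply. Where the date is wholly missing there is no record to contradict, and the return date remains a usable fallback. Where the return date falls inside the recorded month, bounding changes nothing.

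**What to change.** Add one clause to the last-dose rule in SAP 7.3. When the date is partial, impute the earlier of the latest qualifying kit return date and the last day of the recorded month (or of the recorded year, if only the year is known). The result must not be earlier than the first day of that month or year. Leave the rule for a wholly missing date as it is. A cap at date of death may be added for consistency with the AE and medication rules. It would help to list which derivations use the imputed date.

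Do not let a date derived from the tablet count override the others. Missed doses make it too early. A patient who doses through Day 28 but takes 24 of 28 doses (24/28 = 86%) would get Day 24. The Visit 4 limit becomes Day 27, and a genuine on-drug Day 28 sample is lost. At 80% compliance, the lower edge of the SAP's middle category, about 22 doses give Day 22 and a limit of Day 25. The count can also contradict the record: a kit dispensed on 10 March with 15 doses used gives 10 + 15 − 1 = 24 March, even if the last dose is recorded as April. SAP 6.6.1 already has the data ("The quantity of study drug dispensed to and returned by the subject will be counted and recorded on the drug accountability eCRF page"), so the count can serve as a plausibility check or query trigger.

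The cost is a few lines of SAP text and programming, with no new data.

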7.4 Interim Analyses

Further details on the conduct of the interim analysis will be delineated in section 8.10.

7.5 Multi-centre Studies and Pooling of Centres

This study will be a multi-centre study conducted at approximately 10 centres in 3 countries. Approximately one hundred and thirty-eight (138 patients with coronary artery disease (CAD) will be randomized to ensure at least 66 evaluable patients receiving 12 weeks treatment with AZD5718 or placebo.

Given the low number of countries involved in the study (3 in total, Sweden, Denmark and Finland), the unbalance in terms of number of expected randomized subjects per country and the nature of the primary efficacy variable (a quantitative laboratory result, which is expected to be homogenous across countries) randomization was not stratified by country. For the same reason, country will not be included in the statistical model for assessing the efficacy objectives. The same rationale stands for not pooling centres.

Distribution:

Original:

Copy:

TPCA025 Version 2 (based on TPQA036 Version 2) Effective Date: 27th August 2017 Prior Effective Date: 21st December 2016

Sponsor:	AstraZeneca AB	Protocol/CIP Number:	D7550C00003
CIL Project Number:	40343		

7.6 Multiple Comparisons/Multiplicity

Alpha spending function

The study is composed by 4 main endpoints:

- 1. primary endpoint: Change in u-LTE4 at 4 weeks,
- 2. first secondary endpoint: Change in u-LTE₄ at 12 weeks,
- 3. second secondary endpoint: Change in CFVR at 12 weeks,
- 4. third secondary endpoint: Change in CFVR at 4 weeks.

To preserve the overall type1-error at 5% when testing the four endpoints a Hierarchical Procedures will be used (Dmitrienko A. et al 2006). This procedure implies that one will test the four endpoints in a predefined sequence: test of primary endpoint, test of first secondary endpoint, test of second secondary endpoint, test of third secondary endpoint. The test procedure will stop as soon as the first none-significant test, one-sided test at a 5% level, occur and all following test will be declared as non-significant.

Multiplicity test adjustment

All the efficacy and exploratory variables will be assessed for the comparisons of:

AZD5718 versus placebo,
 AZD5718 versus placebo.

AZD5718 comparison versus placebo being included for supporting dose selection in future studies only, meaning that, for all the efficacy and exploratory variables, no adjustment for multiplicity (two groups) is needed.

7.7 Use of an "Efficacy Subset" of Subjects

Not applicable.

7.8 Active-Control Studies Intended to Show Equivalence

Not applicable.

7.9 Examination of Subgroups

Type of MI (STEMI or NSTEMI) is used as a stratification factor in the randomization and will be summarized using descriptive statistics.

Two cohorts of patients will be distinguished:

- Cohort 4w treatment: patients randomized before the CSP v3 implementation, who belong to 4 weeks of treatment
- Cohort 12w treatment: patients randomized after the CSP v3 implementation, who belong to 12 weeks of treatment

Distribution:

Original:

Copy:

TPCA025 Version 2 (based on TPQA036 Version 2)

Sponsor:	AstraZeneca AB	Protocol/CIP Number:	D7550C00003
CIL Project Number:	40343		

Unless otherwise specified, the statistical outputs will be presented jointly for the two cohorts.

8. STATISTICAL ANALYSIS

8.1 Disposition of Subjects

The following summaries will be provided:

- Subject disposition Cohort 4w treatment and Cohort 12w treatment
- Analysis sets (Efficacy Analysis Set and Safety Analysis Set).
- Subject recruitment by region, country and centre for the Efficacy Analysis Set
- Stratification factors by type of MI (STEMI or NSTEMI) Cohort 4w treatment and Cohort 12w treatment - as collected in the IRT for the Efficacy Analysis Set.

The following listings will also be provided:

- A listing of all enrolled subjects who discontinued the study or the treatment.
- A listing of all subjects excluded from the Efficacy Analysis set for all randomized subjects.

The randomization scheme together with the various batches of IP will be listed for all subjects randomized.

8.2 Protocol Deviations

The list of IPDs is provided in the AZ ECD Non-compliance Handling Plan (NHP), version 1.0 or higher. Important protocol deviations (IPDs) will be classified as per AZ ECD Non-compliance Handling Plan. Classified IPDs will be assessed for the Efficacy Analysis Set. The number and percentage of subjects with at least one IPD will be summarized globally and for each category, by treatment group and total.

All subjects reporting IPD will be also listed individually, for all randomized subjects.

8.3 Analysis Populations

There will be 3 analysis populations defined for the study analyses.

8.3.1 Efficacy Analysis Set

The Efficacy Analysis Set for efficacy will be analysed using the intention to treat (ITT) population. This is in accordance to the ICH E9 guideline suggesting that the analysis of the primary endpoint should be analysed according to the treatment to which subjects were actually randomized. The ITT population will include all patients who were randomized, received at least one dose of study medication and have at least one baseline or postbaseline measurement (primary, secondary and exploratory measurements).

Distribution:

Original:

Copy:

TPCA025 Version 2 (based on TPQA036 Version 2) Effective Date: 27th August 2017 Prior Effective Date: 21st December 2016

Sponsor:	AstraZeneca AB	Protocol/CIP Number:	D7550C00003
CIL Project Number:	40343		

8.3.2 Safety Analysis Set

The Safety Analysis Set will include all subjects who were randomized and received at least one dose of study medication. Subjects will be analysed according to the treatment which they actually received. If a subject received IP from the wrong kit for only a part of the treatment duration and then switched to another, the associated treatment group for that subject will be the treatment group that subject was randomized to. Any important deviations from randomized treatment will be listed and considered when interpreting the safety data. Important deviations are defined in section 8.2. The Safety Analysis Set will be used in both demographic (if appropriate) and safety analyses.

